hERG	Human ether-a-go-go related gene
HIV	Human immunodeficiency virus
HSCs	Hematopoietic stem cells
IB	Investigator's Brochure
ICF	Informed consent form
ICF	International conference of harmonization
ID	Intraduodenal
IDS	Investigational Drug Service
IL-6	Interleukin-6
IL-10	Interleukin-10
IND	Investigational New Drug
INR	International normalized ratio
IP	Intraperitoneal
IRB	Institutional review board
ISTH	International Society of Thrombosis and Hemostasis
IU	International unit
IUD	Intrauterine device
IV or iv	Intravenous
KG or kg	Kilogram

LE	Lower extremity
LFA-1	Leukocyte function-associated antigen-1
LFTs	Liver function tests
LMWH	Low molecular weight heparin
m ²	squared
MAC-1	macrophage-1 antigen; CD11b/CD18
MAD	multiple ascending dose
MCRU	Michigan Clinical Research Unit
MICHR	Michigan Institute for Clinical Studies and Health Research
mg	Milligrams
MHC	Major histocompatibility complex
MMP	Matrix metalloproteinase
Min	Minutes
MPs	Microparticles
MPO	Myeloperoxidase
MTD	Maximally tolerated dose
N	Number
NCI	National cancer institute
NETs	Neutrophil endothelial traps
ng	Nanogram
NHP	Non-human primates
NIH	National Institutes of Health
NSAID	Non-steroidal anti-inflammatory drug
PBS	Phosphate buffered saline
PE	Pulmonary embolism
pg	Picogram
PI	Principal investigator
PK	Pharmacokinetics
PMA	Platelet monocyte aggregates
PMNs	Polymorphonuclear leukocytes
PSGL-1	P-Selectin Glycoprotein Ligand 1
PT	Prothrombin time
PTS	Post thrombotic syndrome
QD	Daily
rpm	Revolutions per minute

SAE	Serious Adverse Event
SCD	Sickle Cell Disease
sCD40L	Soluble CD40L
SDF-1	Stromal cell-derived factor 1
SGOT	Serum Glutamic Oxaloacetic Transaminase
SGPT	Serum Glutamic Pyruvic Transaminase
sICAM-1	Soluble intercellular cell adhesion molecule 1
sLe ^x	SialylLewis ^x
sEsel	Soluble E-selectin
sPsel	Soluble P-selectin
SQ or SC	Subcutaneous
SSC	Side scattered light
sTF	Soluble tissue factor
TAT	Thrombin-Antithrombin Complex
TCR	T-cell receptor
TEAE	Treatment-emergent adverse event
TEG	Thromboelastography
TF	Tissue factor
TNF- α	Tumor necrosis factor
TK	Toxicokinetics
Tx	Treatment
ULN	Upper limit of normal
UM	University of Michigan
US	United States
VTE	Venous thromboembolic disease
VEGF	Vascular endothelial growth factor
VTE	Venous thromboembolic disease
VWF	von Willebrand factor
WBC	White blood cells

STUDY SCHEMA

STUDY SYNOPSIS

Title	A Pilot Study to Assess the Safety, Tolerability and Efficacy of Selectin Inhibitor Uproleselan (GMI-1271) in Patients with COVID-19 pneumonia
Phase	Phase I (proof of concept, prospective, interventional, open label single group assignment)
Methodology	Open label with matched de-identified retrospective control cohort
Study Duration	Approximately 24 months
Study Center(s)	Single Center in the United States – University of Michigan, Ann Arbor
Objectives	
Primary Objective:
 
Safety of uproleselan in patients with severe COVID-19 pneumonia.
 
Secondary Objectives:
 
To evaluate if treatment with uproleselan administered intravenously in addition to the best available therapy according to institutional guidelines is able to reduce the progression of acute respiratory failure, in patients with severe COVID-19 pneumonia.
 
 ● To evaluate overall survival and all-cause mortality at day 15 and 28. ● To evaluate changes in the COVID ordinal outcomes scale. ● To assess adverse events to evaluate the safety of uproleselan. ● To assess ventilator-free days, ICU-free days, oxygen, vasopressor free days. ● To evaluate changes in D-dimer. 
Exploratory Objectives:
 
 ● To examine the correlation of plasma soluble E-selectin concentrations with clinical outcomes. ● To examine the correlations of other biomarkers of interest with clinical outcome.
Number of Subjects	15 subjects will be enrolled in the experimental cohort to receive uproleselan. with 1:1 matched de-identified retrospective control cohort. (n=15)
Inclusion Criteria	
 1. Adults, ages 18 – 85 years. 2. Willing and able to provide informed consent prior to performing study procedures unless they have a legally authorized representative (LAR). 3. Documented COVID-19 pneumonia: defined as upper respiratory tract specimen (nasopharyngeal swab (NPS) or viral throat swab) positive for COVID-19 and imaging (CXR/CT scan) suggestive of COVID-19 pneumonia. 4. Confirmed coronavirus (SARS-CoV-2) infection, enrolled ≤ 48 hours of beginning oxygen need for COVID-19+ confirmed hospital admission.

	
 5. Currently hospitalized requiring supplemental oxygen. 6. Have severe COVID-19 according to the World Health Organization (WHO) Interim Guidance with confirmation by real-time RT-PCR assay. The enrollment criteria with one of the following: respiratory distress, respiratory rate (RR) ≥ 30 beats/min; oxygen saturation level less than 93% in resting state; or partial pressure of oxygen (PaO₂)/oxygen concentration (FiO₂) ≤ 300 mmHg. WHO, Clinical management of severe acute respiratory infection when Novel coronavirus (nCoV) infection is suspected: Interim guidance. https://www.who.int/publications-detail/clinical-management-of-severe-acute-respiratory-infectionwhen-novel-coronavirus-(ncov)-infection-is-suspected. 7. Willing and able to participate in all required evaluations and procedures.

Exclusion Criteria
	
 1. In the opinion of at least one investigator, unlikely to survive for >48 hours from screening. 2. Severe chronic respiratory disease (e.g. COPD or other) requiring supplemental oxygen and/or having required mechanical ventilation pre-COVID-19 infection. 3. Concurrent enrollment in a COVID-related interventional drug trial. Use of remdesivir, steroids, and convalescent plasma are permitted along with other standard of care therapies for COVID. 4. Currently on invasive mechanical ventilation. 5. Hypotension defined as systolic blood pressure < 90 mmHg on two sequential readings at least 4 hours apart. 6. Total Bilirubin ≥ 3 x upper limit of normal (ULN), Creatinine Clearance ≤ 30 mL/min/1.73m². 7. Pregnant or breastfeeding. 8. Known diagnosis of an acute thrombosis on admission. 9. Concurrent dual antithrombotic therapy (aspirin or P2Y12 inhibitor plus anticoagulation to treat deep venous thrombosis or pulmonary embolism (single antiplatelet or anticoagulant agent at prophylactic dose is permitted). 10. Concomitant use of thrombolytic therapy. 11. Concomitant therapeutic systemic anticoagulant therapy (e.g. heparin, warfarin, direct thrombin inhibitors and direct factor Xa inhibitors). 12. History of recent major bleeding, defined in accordance with the criteria of the International Society on Thrombosis and Hemostasis (ISTH). 13. History of bleeding disorder thought to impose excessive bleeding risk, as per investigator discretion. 14. Hemodynamic instability, defined as inability to maintain mean arterial pressure. 15. Hypersensitivity to the active substance or to any of the excipients of uproleselan.

	16. Any physical examination findings and/or history of any illness that, in the opinion of the investigator, might confound the results of the study or pose an additional risk to the patient by their participation in the study.
Study Product(s), Dose, Route	Uproleselan 20mg/kg BID, up to a maximum dose of 2500mg, IV infused over 20 minutes on days 1-7.
Duration of Administration	Uproleselan: 20-minute IV infusion BID on days 1-7.
Control	1:1 matched de-identified retrospective control cohort (patients enrolled during the same period with similar severity, not enrolled in another interventional trial, receiving best available therapy according to institutional guidelines).
Statistical Methodology	
This is a pilot proof of concept feasibility study. 15 patients who consent to drug administration will be enrolled in the treatment arm. The sample size determination was not based on statistical power analysis but is large enough to provide adequate information regarding safety, and will contribute to the design of subsequent studies, and is the number of patients that we can expect to accrue in the current setting of the SARS-CoV2 pandemic.
 
Descriptive statistics will be calculated for quantitative safety data, as well as change from baseline. Frequency counts will be compiled for classification of qualitative safety data.
 
Regarding secondary endpoints, the efficacy of uproleselan in prevention of acute respiratory failure, the rate will be calculated as the proportion of patients who experienced at least one of the events above by day+15 from treatment start. The biomarkers will be evaluated for trends at the sample collection time points and contrasted graphically and with simple statistics to the levels observed for control cohort subjects, as the study is not powered for this endpoint.

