3.2 Secondary Endpoints

- Reduction in the progression to acute respiratory failure [Time Frame: 15 days for primary endpoint].
- Patients with a baseline PaO₂/FiO₂ ≥ 200: progression of respiratory failure is defined by:
 - a. severe gas transfer deficit (PaO₂/FiO₂ < 200);
 - b. persistent respiratory distress while receiving oxygen (persistent marked dyspnea, use of accessory respiratory muscles, paradoxical respiratory movements);
- The rate will be calculated as the proportion of patients who experienced at least one of the events above by day+15 from treatment start.

- Reduction in the progression to acute respiratory failure [Time Frame: 28 days].
- Overall survival and all-cause mortality (day 15, day 28).
- Time to improvement in oxygenation for at least 48 hours. Improvement in oxygenation is defined as an increase in PaO₂/FiO₂ of 50 (or greater) compared to the nadir of PaO₂/FiO₂.
- Number of patients requiring mechanical ventilation, if not on mechanical ventilation at study entry.
- Change in the WHO COVID-19, “8-point ordinal scale” from study entry to day 28 (Table 1). To be assessed on day 3, day 8, day 15, day 28.
- Duration of hospitalization and duration of ICU care.
- Toxicity assessment (including incidence of grade 3-5 hemorrhagic events).
- Change in D-dimer [Time Frame: baseline, study day 3, day 8, day 15, and day 28]. Changes in plasma D-dimer level compared with baseline at enrollment.
- Decrease or Change in IL-6:IL-10 ratios.
- Free-Days- at day 28
 - Oxygen
 - Ventilator
 - Vasopressor
 - ICU
 - Hospitalization

Table 1: WHO Ordinal Scale Ordinal Score

Patient State	Descriptor	Score
Ambulatory	No limitation of activities	1
	Limitations of activities	2
Hospitalized (mild disease)	No oxygen therapy	3
	Oxygen by mask or nasal prongs	4
Hospitalized (severe disease)	Non-invasive ventilation or high-flow oxygen	5
	Intubation and mechanical ventilation	6
	Mechanical ventilation + additional organ support – pressors, RRT, ECMO	7
Dead	Death	8

Exploratory Endpoints

- Soluble E-selectin and P-selectin levels compared with baseline at enrollment.
- Thrombosis free days (clinically defined) at day 28.
- Change in other cytokine levels, endothelial or leukocyte activation (day 1, 15, 28) in IL-6, IL-10, Angiopoietin-2, and TNF-alpha

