4.2 Exclusion Criteria

1. In the opinion of at least one investigator, unlikely to survive for >48 hours from screening.
2. Severe chronic respiratory disease (e.g. COPD or other) requiring supplemental oxygen and/or having required mechanical ventilation pre-COVID-19 infection.
3. Concurrent enrollment in a COVID related interventional drug trial. Use of remdesivir, steroids, and convalescent plasma are permitted along with other standard of care therapies for COVID.³⁷
4. Currently on invasive mechanical ventilation.
5. Hypotension defined as systolic blood pressure < 90 mmHg on two sequential readings at least 4 hours apart.
6. Total Bilirubin ≥ 3 x upper limit of normal (ULN), Creatinine Clearance ≤ 30 mL/min/1.73m².
7. Pregnant or breastfeeding.
8. Known diagnosis of an acute thrombosis on admission.
9. Concurrent dual antithrombotic therapy (aspirin or P2Y₁₂ inhibitor plus anticoagulation to treat deep venous thrombosis or pulmonary embolism (single antiplatelet or anticoagulant agent at prophylactic dose is permitted).
10. Concomitant use of thrombolytic therapy.
11. Concomitant therapeutic systemic anticoagulant therapy (e.g. heparin, warfarin, direct thrombin inhibitors and direct factor Xa inhibitors). As per NIH Guidelines: Hospitalized adults with COVID-19 should receive VTE prophylaxis per the standard of care for other hospitalized adults (AIII). Anticoagulant or antiplatelet therapy should not be used to prevent arterial thrombosis outside of the usual standard of care for patients without COVID-19 (AIII); <https://www.covid19treatmentguidelines.nih.gov/therapeutic-management/>
12. History of recent major bleeding, defined in accordance with the criteria of the International Society on Thrombosis and Hemostasis (ISTH).
13. History of bleeding disorder thought to impose excessive bleeding risk as per investigator discretion
14. Hemodynamic instability, defined as inability to maintain mean arterial pressure.
15. Hypersensitivity to the active substance or to any of the excipients of uproleselan.
16. Any physical examination findings and/or history of any illness that, in the opinion of the investigator, might confound the results of the study or pose an additional risk to the patient by their participation in the study

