5.4 Duration of Therapy

Each subject in the treatment arm will receive one dose of uproleselan every 12 hours (12 hours apart optimally; acceptable range 10-14 hours) on treatment days 1-7.

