6.1.1 Procedures during Study Drug Treatment Visits

If a laboratory parameter has been obtained within 48 hours prior to study enrollment, it does not need to be repeated for study purposes and will be considered the *baseline* value. Following the last day of study, no further “study related” blood tests will be obtained.

Guidelines for monitoring hematologic and coagulation parameters were derived from Thachil, J., et al., *ISTH interim guidance on recognition and management of coagulopathy in COVID-19*. *J Thromb Haemost*, 2020. **18**(5): p. 1023-1026.⁴²

- **Pulmonary Indices:** Pulmonary parameters will be recorded daily for subjects from the time of study entry to cessation of study drug therapy. Pulmonary assessment will include a subject’s current level of supplemental oxygen support (%FiO₂), current modality of support (mechanical ventilation, BiPaP, CPAP, nasal cannula, or none), and the results of any chest radiographs (if performed) that day. For patients that remain hospitalized on day 15 or 28 of study, pulmonary indices will also be made at that time point. Blood gas values will be obtained as clinically indicated. Scoring from the WHO COVID Ordinal Scale (Table 1) will be determined as indicated by study investigators or study coordinators.
- **Hematologic parameters:**
A complete blood count including platelets (CBCP) should be obtained at baseline (study entry), and daily until cessation of study therapy. Additional blood counts may be obtained as clinically indicated.
- **Chemistries:**
Serum chemistries (Electrolytes, BUN, creatinine, liver panel) should be obtained at baseline (study entry), and daily until cessation of study therapy. Additional chemistries should be obtained as clinically indicated.
- **Coagulation Labs:**
D-dimer, Prothrombin time (PT), activated partial thromboplastin time (aPTT), and serum fibrinogen should be obtained at baseline (study entry). Additional D-dimer, PT, and serum fibrinogen testing may be obtained as clinically indicated.
- **Serologic Cytokine Profiles:** Biomarkers will be drawn on day 0-1 pre-study drug administration, days 1-7, day 15, and day 28. These will be used to measure e-selectin levels and are not for safety labs. Due to current hospital understaffing, blood draws will occur as staffing permits. Missed blood draws will not be counted as protocol deviations.

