- g. Study blood draws, including D-dimer and biomarkers, will only occur if patient is still hospitalized and as hospital staffing permits (weekends/holidays may not be feasible). No outpatient study blood draws will be performed.

Table 5: Parameters to be Tested for Hematology, Serum Chemistry, and Coagulation Studies

Category	Parameters
Hematology	Hematocrit, hemoglobin, mean corpuscular hemoglobin (MCH), mean corpuscular hemoglobin concentration (MCHC), mean corpuscular volume (MCV), platelets, mean platelet volume, red blood cells (RBCs), white blood cells (WBCs) with complete differential including neutrophils, lymphocytes, monocytes, basophils, eosinophils, immature granulocytes
Serum chemistry	Comprehensive metabolic panel (CMP) to include: total protein, albumin, alkaline phosphatase, ALT/SGPT, AST/SGOT, total bilirubin, BUN, creatinine, estimated glomerular filtration rate (EGFR) (ml/min), electrolytes (sodium, potassium, calcium, chloride, bicarbonate), and glucose
Coagulation	Prothrombin time (PT), international normalized ratio (INR), activated partial thromboplastin time (aPTT), fibrinogen

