9 DRUG INFORMATION

9.1 Uproleselan Injection, 50 mg/mL

Other Names for the Drug: GMI-1271

Description: Uproleselan injection is a sterile solution for IV administration, supplied in single-dose vials at a concentration of 50 mg/mL.

Classification - Type of Agent: small molecule E-selectin antagonist

Mode of Action: E-selectin antagonist

Pharmacokinetics: PK evaluations in healthy volunteers showed a dose-linear relationship in mean PK parameters after IV infusion of uproleselan 2 mg/kg, 5 mg/kg, 10 mg/kg, 20 mg/kg, and 40 mg/kg. Uproleselan is characterized by a half-life of 1.4 to 2.5 hours and does not accumulate after doses up to 20 mg/kg twice daily. Population PK analysis in healthy volunteers and subjects with AML demonstrates similar PK profiles, PK parameters, and dose-proportionality. Clearance was found to depend on renal function and have a similar magnitude in both healthy volunteers and in subjects with AML. Clearance is not dependent on body size which allows for flat-fixed dosing. The PK of uproleselan does not appear to be affected when co-administered with chemotherapy. Uproleselan is predominantly (>95%) excreted unchanged in the urine and is not extensively metabolized in humans. Refer to the uproleselan IB for further information.

Side Effects: No adverse events were seen during pre-clinical testing. The safety and efficacy of uproleselan have not been fully established. However, limited human safety information is available from Phase 1 clinical trials in healthy volunteers and subjects with DVT, MM, and a Phase 1/2 clinical trial in subjects with AML. No specific toxicities, or target organs for toxicity, have been identified thus far in nonclinical studies or in clinical trials for uproleselan. This includes administration alone or with cytarabine-based chemotherapy regimens for AML. In healthy volunteer studies, no trends in routine lab evaluation such as hematology, chemistry, coagulation, urinalysis, electrocardiogram (ECG) and bleeding time were observed. Clinical trials are ongoing. Refer to the uproleselan IB for further information.

Drug Interactions: No known drug interactions

Uproleselan (GMI-1271) Supply and Storage

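### Uproleselan is renally cleared and low creatinine clearance bars entry, yet no on-treatment renal value holds a dose, and 8.2.1 is unclear on worsening of already abnormal laboratory values

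*Combined protocol and SAP*

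**What the plan says.** **Dosing.** The Study Synopsis gives the regimen as "Uproleselan 20mg/kg BID, up to a maximum dose of 2500mg, IV infused over 20 minutes on days 1-7". Table 2 in 5.1.1 gives the same dose, and 5.4 adds "Each subject in the treatment arm will receive one dose of uproleselan every 12 hours" on treatment days 1 to 7. None of these attaches a renal condition, and there is no dose-modification section.

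**Pharmacokinetics.** Section 9.1 states "Uproleselan is predominantly (>95%) excreted unchanged in the urine and is not extensively metabolized in humans" and "Clearance was found to depend on renal function".

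**Entry.** Exclusion 6 in 4.2 bars "Creatinine Clearance ≤ 30 mL/min/1.73m²". It names no formula and gives no reason for the limit.

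**Monitoring.** Section 6.1.1 says "Serum chemistries (Electrolytes, BUN, creatinine, liver panel) should be obtained at baseline (study entry), and daily until cessation of study therapy". Table 5 in 6.2 includes "estimated glomerular filtration rate (EGFR) (ml/min"), a different unit from the entry limit. No action follows from either value.

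**Stopping.** Section 5.6 lets the investigator or treating physician take a patient off study for safety, for an adverse event or in the patient's interest. Safety procedures then continue where possible, and 5.7 replaces patients who are removed. The named triggers in section 13 are major bleeding and early mortality.

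**Adverse events.** Section 8.2.1 counts an increase in the severity of a pre-existing condition as an AE. The same section then lists, among laboratory findings that need not be reported, those outside the reference range at screening. It does not say what happens if they worsen.

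**The concern.** Safety is the primary endpoint and there are 15 treated patients. The protocol recognises renal decline in this disease: 1.1 lists kidney injury among risk factors for poor outcome, and 1.2 mentions renal microcirculatory impairment. A patient whose clearance falls below the entry limit on day 3 is, as written, still scheduled for full doses. Two such patients could be handled differently depending on who decides. The only written way to stop the drug is removal from the study, whereas a temporary hold would keep the patient's safety record on schedule.

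The AE wording adds a second problem. A creatinine raised at screening that then worsens fits both the rule that counts it and the rule that exempts it. The same change could be an AE in one patient and go unrecorded in another. This applies to any laboratory parameter, not only renal ones.

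**Working it through.** The plan states no figure to reproduce. The check has four parts.

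**1. Schedule.** 2 infusions × 7 days = 14. A fall seen before dosing on day 3 leaves 5 × 2 = 10 still scheduled. The largest daily dose is 2 × 2500 = 5000 mg, under the overdose line of 5500 mg per 24 hours in 9.1, so full dosing in renal failure would not be flagged there either.

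**2. Exposure.** From the documents: more than 95% of the drug is excreted unchanged in urine (9.1), and the mean non-clinical margin is 5-fold at 20 mg/kg (1.3). Assumed: a fraction f of drug clearance, 0.95 to 1.0, is proportional to creatinine clearance; the margin is an AUC ratio; and the reference clearance (ref) behind it is 60 to 120 mL/min, because the documents give none.

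Relative AUC = 1 / ((1 − f) + f × CrCl/ref)

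| CrCl (mL/min) | ref 60 | ref 90 | ref 120 |
|---|---|---|---|
| 30 | 1.9–2.0 | 2.7–3.0 | 3.5–4.0 |
| 20 | 2.7–3.0 | 3.8–4.5 | 4.8–6.0 |
| 15 | 3.5–4.0 | 4.8–6.0 | 5.9–8.0 |

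At 20 mL/min the extremes are 1/(0.05 + 0.95 × 20/60) = 2.73 and 120/20 = 6.0. The remaining margin is 5/2.73 = 1.8 down to 5/6.0 = 0.8. Relative AUC reaches 5 at CrCl = ref × (0.2 − (1 − f))/f: 9.5 to 12.0 mL/min for ref 60, and 18.9 to 24.0 for ref 120.

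If volume is constant, the 1.4 to 2.5 hour half-life in 9.1 scales by the same factor. At 20 mL/min it becomes 1.4 × 2.73 = 3.8 hours up to 2.5 × 6.0 = 15 hours. Accumulation at 12-hourly dosing, 1/(1 − exp(−ln 2 × 12/half-life)), is then 1.13 to 2.35. The statement in 9.1 that the drug does not accumulate would not carry over.

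**3. Human precedent.** By 1.3, 21 people received 20 mg/kg (13 volunteers and 8 patients) and four volunteers received 40 mg/kg, with no SAE at 40 mg/kg. Since 9.1 reports dose-linear PK to 40 mg/kg, about 40/20 = 2 times the 20 mg/kg exposure has been reached. The 2.7 to 6.0 range lies above that.

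**4. Frequency.** The documents give none. If each patient had an assumed 2% to 20% chance of crossing the limit, the chance of at least one in 15 would be 1 − 0.98^15 = 26% to 1 − 0.80^15 = 97%. That range is too wide to say more than that it could happen.

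**The case against.** The strongest case is that no harm has been shown and discretion already covers this. Section 1.3 says safety did not depend on exposure across 5, 10 and 20 mg/kg every 12 hours in the AML study, and 9.1 identifies no target organ. Patients are inpatients at one centre, creatinine is seen daily, and under section 14 an independent medical monitor and the investigators review laboratory data. All of this stands and limits the point. It does not supply a threshold, and the human data do not reach the exposures computed above.

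Four stronger readings are tempting, and the documents do not support them.

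- *That using up the 5-fold margin means toxicity.* By 1.3 the no-effect level was the highest dose tested in both species, so it marks where the animal data end.
- *That the sponsor set 30 as an exposure limit.* No reason is given, and the same exclusion bars raised bilirubin although the drug is not extensively metabolised. Nor does an entry exclusion automatically end dosing: invasive ventilation bars entry, yet 6.1.1 records it as a support mode during treatment.
- *That a patient taken off the drug is lost to the safety data.* Section 5.2 keeps every treated patient evaluable for toxicity, and 8.2.1 collects serious and protocol-defined AEs for 28 days.
- *That the outcome scale shows the plan expects dialysis.* Its score 7, "Mechanical ventilation + additional organ support – pressors, RRT, ECMO", counts RRT only alongside mechanical ventilation.

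On laboratory values, the exemption in 8.2.1 is permissive, and an investigator could still report a worsened condition. That leaves the choice open rather than resolving it. The Investigator's Brochure and pharmacy manual were not available, so renal guidance there cannot be ruled out.

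**Conclusion.** The point holds as a moderate gap in safety conduct. No written rule links the daily renal result to dosing, so stopping after a decline is discretionary and runs through removal from the study. The possible exposure at 20 mL/min is about 2.7 to 6.0 times reference. That rests on drug clearance tracking creatinine clearance, a 60 to 120 mL/min reference, and the margin being an AUC ratio. The documents establish neither harm at that exposure nor how often it would arise.

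The AE-reporting conflict is a separate point. It needs none of these assumptions, and it bears directly on counts for the primary endpoint.

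**What to change.** 1. In 5.1.1 and 5.4, name one renal formula, in mL/min/1.73m², for both the entry criterion and the daily check. Hold uproleselan while the value is 30 or less or the patient is on dialysis. Resume when it is above 30 and the patient is off dialysis. Held doses are not made up, and dosing ends on day 7. State that a hold is neither cessation of study therapy under 6.1.1 nor removal under 5.7. Daily chemistries, follow-up and inclusion in the safety analysis then continue, and the patient is not replaced. Section 8.7 already stops the drug but keeps safety follow-up for pregnancy.
2. In 8.2.1, state that a laboratory value abnormal at screening is reported as an AE if it worsens by one or more CTCAE grades.
3. In 12.3, list held doses beside each patient's AEs, as description only.

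**Cost.** No new test is needed, since creatinine and eGFR are already in the panel; the formula and unit have to be settled. Some patients will miss doses, and creatinine lags true clearance, so a hold can come late. More laboratory AEs may be recorded.

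**Limit.** The rule caps exposure but does not normalise it. At exactly 30 mL/min, relative AUC is still 1.9 to 4.0. For an assumed patient of 125 kg and 175 cm (Mosteller surface area 2.465 m²), 30 indexed is 30 × 2.465/1.73 = 42.7 mL/min. At 2500 mg against the 1400 mg of a 70 kg patient, relative AUC there is about 2.5 to 5.0, from (2500/1400)/(0.05 + 0.95 × 42.7/60) to (2500/1400)/(42.7/120). The sponsor can judge from its own population PK model whether a higher tier is needed.
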